5.1.6 Laboratory Requirements (must be done within 7 days prior to registration)

Hematology:	Absolute neutrophils (ANC)	$\geq 1.5 \times 10^9/L$
	Platelets	$\geq 100 \times 10^9/L$
	Hemoglobin	$\geq 90 \text{ g/L}$ or $\geq 5.6 \text{ mmol/L}$ (without transfusion or EPO dependency)
Chemistry:	Serum creatinine	$\leq 1.5 \times \text{ULN}$
	OR	OR
	Measured or calculated creatinine clearance	$\geq 60 \text{ mL/min}$ for subject with creatinine levels $> 1.5 \times \text{ULN}$
	Serum Total Bilirubin	$\leq 1.5 \times \text{ULN}$
	OR	OR
	Direct bilirubin	$\leq \text{ULN}$ for subjects with total bilirubin levels $> 1.5 \times \text{ULN}$
	AST and ALT	$\leq 2.5 \times \text{ULN}$ ($\leq 5 \times \text{ULN}$ for subjects with liver mets)
	Albumin	$\geq 25 \text{ g/L}$

5.1.7 Women/men of childbearing potential must have agreed to use a highly effective contraceptive method. A woman is considered to be of "childbearing potential" if she has had menses at any time in the preceding 12 consecutive months. In addition to routine contraceptive methods, "effective contraception" also includes heterosexual celibacy and surgery intended to prevent pregnancy (or with a side-effect of pregnancy prevention) defined as a hysterectomy, bilateral oophorectomy or bilateral tubal ligation, or vasectomy/vasectomized partner. However, if at any point a previously celibate patient chooses to become heterosexually active during the time period for use of contraceptive measures outlined in the protocol, he/she is responsible for beginning contraceptive measures.

5.1.8 Women of childbearing potential will have a serum or urine pregnancy test within 7 days prior to registration to determine eligibility. If the urine test is positive or cannot be confirmed as negative, a serum pregnancy test will be required. This may also include an ultrasound to rule-out pregnancy if a false-positive is suspected. For example, when beta-human chorionic gonadotropin is high and partner is vasectomized, it may be associated with tumour production of hCG, as seen with some cancers. Patient will be considered eligible if an ultrasound is negative for pregnancy.

AMEND #2: 2017-JUL-10

5.1.9 Patient consent must be obtained according to local Institutional and/or University Human Experimental Committee requirements. It will be the responsibility of the local participating investigators to obtain the necessary local clearance, and to indicate in writing to the CCTG Study Coordinator that such clearance has been obtained, before the trial can commence in that centre. Because of differing requirements, a standard consent form for the trial will not be provided but a sample form is provided on the IND.225 webpage. A copy of the initial REB approval and approved consent form must be sent to the central office. The patient must sign the consent form prior to registration and prior to tests which are considered to be study specific (see Section 6). Please note that the consent form for this study must contain a statement which gives permission for the CCTG and monitoring agencies to review patient records.

Patients who cannot give informed consent (i.e. mentally incompetent patients, or those physically incapacitated such as comatose patients) are not to be recruited into the study. Patients competent but physically unable to sign the consent form may have the document signed by their nearest relative or legal guardian. Each patient will be provided with a full explanation of the study before consent is requested.

5.1.10 Patients must be accessible for treatment and follow-up. Patients registered on this trial must be treated and followed at the participating centre. This implies there must be reasonable geographical limits (for example: 1 ½ hour's driving distance) placed on patients being considered for this trial. (Call the CCTG office [contact]) if questions arise regarding the interpretation of this criterion.) Investigators must assure themselves the patients registered on this trial will be available for complete documentation of the treatment, adverse events, and follow-up.

5.1.11 In accordance with CCTG policy, protocol treatment is to begin within 2 working days of patient registration.

5.2 Ineligibility Criteria

Patients who fulfill any of the following criteria are not eligible for admission to the study:

5.2.1 Patients who have received prior systemic treatment for metastatic melanoma.

5.2.2 Patients with known history of Human Immunodeficiency Virus (HIV) (HIV 1/2 antibodies).

5.2.3 Patients with a known history of or known positive for Hepatitis B (HBsAg reactive) or Hepatitis C (HCV RNA [qualitative] is detected). Patients with unknown history of HBV or HCV will require screening.

5.2.4 Patients with previously treated brain metastases may participate provided they are stable with no evidence of enlargement following radiation treatment and no acute radiation toxicity OR no evidence of enlargement at least 4 weeks prior to the first dose of study drug if untreated and are off systemic steroids for at least two weeks.

5.2.5 Patients who are pregnant or breastfeeding, or expecting to conceive or father children within the projected duration of the study, starting with the pre-screening or screening visit through 4 months after the last dose of trial treatment.

5.2.6 Patients who previously had a severe hypersensitivity reaction to treatment with another mAb.

AMEND #1: 2016-NOV-23

- 5.2.7 Patients with an active autoimmune disease or a documented history of autoimmune disease or syndrome that requires systemic steroids or immunosuppressive agents. (Only patients on active treatment are ineligible).
- 5.2.8 Patients with a history of a malignancy (other than the disease under treatment in the study) within 5 years prior to first study drug administration.
- 5.2.9 Patients on any systemic corticosteroid therapy within one week before the planned date for first dose of treatment or on any other form of immunosuppressive medication.
- 5.2.10 Patients with an allergy to iodinated contrast media used for CT.
- 5.2.11 Patients with a known history of active TB (Bacillus Tuberculosis).
- 5.2.12 Patients with evidence of interstitial lung disease.
- 5.2.13 Patients with known history of, or any evidence of active, non-infectious pneumonitis.

AMEND #1: 2016-NOV-23; AMEND #2: 2017-JUL-10

6.0 PRE-TREATMENT EVALUATION
(See Appendix I)

Investigations		Timing
History and Physical Exam including:	
 history height/weight vital signs (blood pressure and pulse) ECOG performance status documentation of all measurable and non-measurable disease clinical tumour measurements (if applicable) 	Within 14 days prior to registration
Hematology	
 CBC, differential, platelets 	Within 7 days prior to registration
Biochemistry	
 serum creatinine (or measured or calculated creatinine clearance) electrolytes (sodium, potassium, chloride, bicarbonate) bilirubin alkaline phosphatase AST, ALT LDH phosphorous calcium magnesium albumin TSH, FT3, FT4 HCV, HBV screening serology (if unknown) 	Within 7 days prior to registration
Radiology ¹	
 CT scan with contrast of chest, abdomen/pelvis other sites as clinically indicated 	Within 28 days ² prior to registration
Other Investigations	
 pregnancy test* (if applicable) ECG (if not done within 6 months) 	Within 7 days prior to registration
Economics	
 Health Utilities Index (EQ-5D) 	
Adverse Event ³	
 baseline adverse event evaluation (to document residual adverse event from previous therapy and baseline symptoms) 	

1 To ensure comparability, baseline and subsequent CT scans to assess response must be performed using identical techniques (i.e. scans performed immediately following bolus contrast administration using a standard volume of contrast, the identical contrast agent, and preferably the same scanner – see Appendix VII).
 2 Thirty-five days if negative
 3 Adverse events will be recorded and graded according to the NCI Common Terminology Criteria for Adverse Events (CTCAE) (Appendix V).
 * These tests are considered study-specific and must be performed AFTER the informed consent form has been signed.

7.0 ENTRY/REGISTRATION PROCEDURES

7.1 Entry Procedures

All registrations will be done through the CCTG web-based, password-operated Electronic Data Capture (EDC) system. Complete details regarding obtaining a password, accessing the system and registering patients will be provided at the time of study activation and will also be included in the “EDC Data Management Guidebook”, posted on the IND.225 trial specific web-site. If sites experience difficulties accessing the system and/or registering patients please contact the help desk (link in EDC) or the IND.225 Study Coordinator.

All eligible patients enrolled on the study by the participating treatment centre will be assigned a serial number which must be used on all documentation and correspondence with CCTG.

The following information will be required:

- trial code (CCTG IND.225)
- patient's initials (may be coded)
- informed consent version date, date signed by patient, name of person conducting consent discussion and date signed
- confirmation of the requirements listed in Section 5.0, including dates of essential tests and actual laboratory values
- height and weight

7.2 Registration

Registrations will be provided electronically.

Note: The validity of results of the trial depends on the authenticity of and the follow-up of all patients entered into the trial. Under no circumstances, therefore, may an allocated patient's data be withdrawn prior to final analysis, unless the participant withdraws from the trial and requests that data collection/submission cease from the point in time of withdrawal.

All eligible patients admitted to the trial will be followed by the coordinating centre. It is the responsibility of the physician in charge to satisfy himself or herself that the patient is indeed eligible before requesting registration.

All patients are to be followed until death or until sites are informed by CCTG that further follow-up is no longer required.

8.0 TREATMENT PLAN

Although the Canadian Cancer Trials Group acts as the coordinating agency for the trial, the responsibility for treatment of patients rests with the individual investigator.

In accordance with CCTG policy, protocol treatment is to begin within 2 working days of patient registration.

8.1 Chemotherapy Treatment Plan

8.1.1 Drug Administration

Agent	Route	Starting Dose	Schedule
Pembrolizumab	IV	200 mg	Day 1 every 3 weeks

8.2 Dose Adjustments for Pembrolizumab

Pembrolizumab will be withheld for drug-related Grade 4 hematologic toxicities, non-hematological toxicity \geq Grade 3 including laboratory abnormalities, and severe or life threatening AEs as per Table below.

The guidelines that follow outline dose adjustments for several of these toxic effects. If a patient experiences several adverse events and there are conflicting recommendations, please use the recommended dose adjustment that requires the greatest dose hold or discontinuation.

Dosing interruptions are permitted in the case of medical / surgical events or logistical reasons not related to study therapy (e.g. elective surgery, unrelated medical events, patient vacation, and/or holidays). Subjects should be placed back on study therapy within 3 weeks of the scheduled interruption, unless otherwise discussed with the Sponsor. The reason for interruption should be documented in the patient's study record.

The following general guidance should be followed for management of toxicities:

1. Treat each of the toxicities with maximum supportive care (including slowing / interrupting / omitting the agent suspected of causing the toxicity where required).
2. If the symptoms promptly resolve with supportive care, consideration should be given to continuing the same dose of pembrolizumab along with appropriate continuing supportive care.

In addition to the dose adjustments shown in this section, the following are recommended:

- Patient evaluation to identify any alternative etiology.
- In the absence of a clear alternative etiology, all events of an inflammatory nature should be considered to be immune-related.
- Symptomatic and topical therapy should be considered for low-grade events.
- For persistent (greater than 3 to 5 days) low-grade (Grade 2) or severe (Grade \geq 3) events promptly start prednisone PO 1-2 mg/kg/day or IV equivalent.

Admin Update #1: 2016-MAY-10

- If symptoms recur or worsen during corticosteroid tapering (> 4 weeks of taper), increase the corticosteroid dose [prednisone dose [e.g. up to 2-4 mg/kg/day or IV equivalent]] until stabilization or improvement of symptoms, then resume corticosteroid tapering at a slower rate.
- More potent immunosuppressive drug (refer to individual sections of the immune related adverse event for specific type of immunosuppressive drugs) should be considered for events not responding to systemic steroids.
- Discontinuation of study drug is not mandated for Grade 3 / Grade 4 inflammatory reactions attributed to local tumour response (e.g. inflammatory reaction at sites of metastatic disease, lymph nodes etc.). Continuation of study drug in this situation should be based upon a benefit/risk analysis for that patient and be discussed with CCTG.

8.3 Dose Modification Guidelines for Drug-related Adverse Events

Toxicity	Hold Treatment For Grade	Timing for Restarting Treatment	Treatment Discontinuation
Diarrhea/Colitis	2-3	Toxicity resolves to Grade 0-1	Toxicity does not resolve within 12 weeks of last dose or inability to reduce corticosteroid to 10 mg or less of prednisone or equivalent per day within 12 weeks
	4	Permanently discontinue	Permanently discontinue
AST, ALT, or Increased Bilirubin	2	Toxicity resolves to Grade 0-1	Toxicity does not resolve within 12 weeks of last dose
	3-4	Permanently discontinue (see exception below) ^a	Permanently discontinue
Type 1 diabetes mellitus (if new onset) or Hyperglycemia	T1DM or 3-4	Hold pembrolizumab for new onset Type 1 diabetes mellitus or Grade 3-4 hyperglycemia associated with evidence of beta cell failure. Insulin replacement therapy is recommended for Type I diabetes mellitus and for grade 3-4 hyperglycemia associated with metabolic acidosis or ketonuria.	Resume pembrolizumab when patients are clinically and metabolically stable
Hypophysitis	2-4	Toxicity resolves to Grade 0-1. Therapy with pembrolizumab can be continued while endocrine replacement therapy is instituted. When symptoms improve to grade 1 or less, steroid taper should be started and continued over no less than 4 weeks.	Toxicity does not resolve within 12 weeks of last dose or inability to reduce corticosteroid to 10 mg or less of prednisone or equivalent per day within 12 weeks

table continued on next page ...

Admin Update #1: 2016-MAY-10

Toxicity	Hold Treatment For Grade	Timing for Restarting Treatment	Treatment Discontinuation
Hyperthyroidism	3	Toxicity resolves to Grade 0-1	Toxicity does not resolve within 12 weeks of last dose or inability to reduce corticosteroid to 10 mg or less of prednisone or equivalent per day within 12 weeks
	4	Permanently discontinue	Permanently discontinue
Hypothyroidism		Therapy with pembrolizumab can be continued while thyroid replacement therapy is instituted	Therapy with pembrolizumab can be continued while thyroid replacement therapy is instituted
Infusion Reaction	2 ^b	Toxicity resolves to Grade 0-1	Permanently discontinue if toxicity develops despite adequate premedication
	3-4	Permanently discontinue	Permanently discontinue
Pneumonitis	2	Toxicity resolves to Grade 0-1. For grade 2 events treat with systemic corticosteroids. When symptoms improve to grade 1 or less, steroid taper should be started and continued over no less than 4 weeks.	Toxicity does not resolve within 12 weeks of last dose or inability to reduce corticosteroid to 10 mg or less of prednisone or equivalent per day within 12 weeks
	3-4	Permanently discontinue	Permanently discontinue
Renal Failure or Nephritis	2	Toxicity resolves to Grade 0-1	Toxicity does not resolve within 12 weeks of last dose or inability to reduce corticosteroid to 10 mg or less of prednisone or equivalent per day within 12 weeks
	3-4	Permanently discontinue	Permanently discontinue
All Other Drug-Related Toxicity	3 or Severe	Toxicity resolves to Grade 0-1	Toxicity does not resolve within 12 weeks of last dose or inability to reduce corticosteroid to 10 mg or less of prednisone or equivalent per day within 12 weeks
	4	Permanently discontinue	Permanently discontinue

Note: Permanently discontinue for any severe or Grade 3 drug-related AE that recurs or any life-threatening event.

^a For patients with liver metastasis who begin treatment with Grade 2 AST or ALT, if AST or ALT increases by greater than or equal to 50% relative to baseline and lasts for at least 1 week then patients should be discontinued.

^b If symptoms resolve within one hour of stopping drug infusion, the infusion may be restarted at 50% of the original infusion rate (e.g., from 100 mL/hr to 50 mL/hr). Otherwise dosing will be held until symptoms resolve and the subject should be premedicated for the next scheduled dose; Refer to Section 8.3.1, Infusion Related Reactions Table for further management details.

^c Patients with intolerable or persistent Grade 2 drug-related AE may hold study medication at physician discretion. Permanently discontinue study drug for persistent Grade 2 adverse reactions for which treatment with study drug has been held, that do not recover to Grade 0-1 within 12 weeks of the last dose.

Where appropriate, these guidelines include the use of oral or intravenous treatment with corticosteroids as well as additional anti-inflammatory agents if symptoms do not improve with administration of corticosteroids. Note that several courses of steroid tapering may be necessary as symptoms may worsen when the steroid dose is decreased. For each disorder, attempts should be made to rule out other causes such as metastatic disease or bacterial or viral infection, which might require additional supportive care. The treatment guidelines are intended to be applied when the investigator determines the events to be related to pembrolizumab.

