- Patients with an active autoimmune disease or a documented history of autoimmune disease or syndrome that requires systemic steroids or immunosuppressive agents;
- Patients with a history of a malignancy (other than the disease under treatment in the study) within 5 years prior to first study drug administration;
- Patients on any systemic corticosteroid therapy within one week before the planned date for first dose of treatment or on any other form of immunosuppressive medication;
- Patients with an allergy to iodinated contrast media used for CT;
- Patients with a known history of active TB (Bacillus Tuberculosis);
- Patients with evidence of interstitial lung disease;
- Patients with known history of, or any evidence of active, non-infectious pneumonitis.

Pre-Treatment Evaluations

- History, physical exam, ECOG performance status, vital signs, toxicity/baseline symptoms (within 14 days prior to registration);
- Hematology and biochemistry (within 7 days prior to registration);
- Pregnancy test (within 7 days prior to registration, if applicable);
- ECG (within 7 days prior to registration if not done within 6 months);
- Health Utilities Index (EQ-5D) (within 7 days prior to registration);
- CT scan with contrast of chest, abdomen/pelvis (within 28 days prior to registration; 35 days if negative).

Treatment

- Pembrolizumab will be given intravenously day 1 every 3 weeks

On-Treatment Evaluations

- History and physical exam, ECOG (Day 1 each cycle)
- Vital signs (blood pressure and pulse) (Day 1 each cycle)
- Hematology and Biochemistry (Day 1 each cycle)
- TSH, FT3, FT4 (every other cycle)
- CT scan with contrast of chest, abdomen/pelvis (4 weeks, 12 weeks, then every 12 weeks)
- ECG (as clinically indicated)
- Health Utilities Index (EQ-5D) and Resource Utilization Assessment (each 12 weekly visit until progression OR maximum 1 year from registration)
- Adverse events – patients to be evaluated continuously for adverse events.

Duration of Treatment

See Section 12.

AMEND #1: 2016-NOV-23

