8.5 Concomitant Therapy

8.5.1 Permitted

Patients may receive ongoing supportive and palliative care (e.g. pain control) as clinically indicated throughout the study. Physiological doses of systemic corticosteroids are allowed, as well as inhaled, topical and prophylaxis use for allergic reactions, such as IV contrast dye. All supportive medications must be recorded on the electronic case report form as appropriate.

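### Section 8.3 holds pembrolizumab for drug-related new-onset T1DM or Grade 3-4 hyperglycemia with evidence of beta cell failure, but no chemistry list requires a glucose test

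*Combined protocol and SAP*

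**What the plan says.** The protocol's rules on holding drug:

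- Section 8.3, in the row for type 1 diabetes and hyperglycemia, says: "Hold pembrolizumab for new onset Type 1 diabetes mellitus or Grade 3-4 hyperglycemia associated with evidence of beta cell failure". The neighbouring cell, which gives the grade that triggers a hold, names only T1DM or Grades 3-4 and does not mention beta cell failure.
- Section 8.2 has a general rule that withholds drug for drug-related non-hematological toxicity at or above "Grade 3 including laboratory abnormalities, and severe or life threatening AEs as per Table below".
- The text after the 8.3 table limits all of this to drug-related events: "The treatment guidelines are intended to be applied when the investigator determines the events to be related to pembrolizumab".

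The protocol's laboratory schedule:

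- The summary says only "Hematology and Biochemistry (Day 1 each cycle") and names no analytes.
- The baseline biochemistry list in 6.0 begins with "serum creatinine (or measured or calculated creatinine clearance") and continues through electrolytes, liver tests, LDH, minerals, albumin, thyroid tests and hepatitis serology. Glucose is not in it.
- Section 9.1 schedules electrolytes, alkaline phosphatase, AST, ALT, creatinine and bilirubin on Day 1 of each cycle, and thyroid tests every other cycle. Its as-needed tier names phosphorous, calcium, magnesium and albumin. Glucose is in neither.
- Appendix I repeats these lists, again without glucose. HbA1c, urinalysis and ketones are not listed anywhere.

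**The concern.** The protocol treats new-onset diabetes, and hyperglycemia with evidence of beta cell failure, as reasons to stop dosing. The first sign of either in a patient without symptoms would be a raised glucose, and no site is required to measure it. A site could follow the schedule exactly and give the next dose without that information.

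A baseline value matters as well. The row concerns new onset, and the guidelines apply only to events judged related to pembrolizumab. Section 5.2 does not exclude diabetes by name, so patients with raised glucose at entry can be enrolled. The protocol's own management of immune-related events is another source of raised glucose: for persistent Grade 2 or for Grade 3 and higher events, 8.2 says to "promptly start prednisone PO 1-2 mg/kg/day or IV equivalent". Without a baseline and serial values, pre-existing, steroid-related and drug-related hyperglycemia are harder to tell apart.

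What is at stake is patient safety and, second, the toxicity objective in 1.2. The laboratory tabulation promised in 14.3 would contain no scheduled glucose result.

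**Working it through.** The plan states no figure on this point, so the check sets the hold rows beside the schedule and counts scheduled results.

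**Inputs.** Three-week cycles (8.1.1); protocol treatment for at most one year (12.2); 84 patients to be recruited (14.2); test frequencies from 6.0, 9.1 and Appendix I.

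**Day 1 visits in one year.** Weeks 0, 3, ..., 51, so 51/3 + 1 = 18.

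**Scheduled results per patient.** Baseline plus on treatment:

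| Hold row in 8.3 | Test behind it | Baseline (6.0) | On treatment (9.1) | Maximum results |
|---|---|---|---|---|
| AST, ALT or bilirubin | same | yes | Day 1, each cycle | 1 + 18 = 19 each |
| Renal failure or nephritis | creatinine | yes | Day 1, each cycle | 1 + 18 = 19 |
| Hyperthyroidism | TSH, FT3, FT4 | yes | every other cycle | 1 + 18/2 = 10 each |
| Hypophysitis | thyroid tests in part; no cortisol or ACTH listed | in part | in part | 10 for the thyroid part, 0 for the rest |
| T1DM or hyperglycemia | glucose | no | no | 0 |

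**What could reveal a case without glucose.** Section 9.1 provides history and physical examination on Day 1, adverse event review each cycle, and bicarbonate on Day 1. The first two depend on symptoms or signs, and bicarbonate depends on acidosis. None detects a raised glucose in a patient who is neither symptomatic nor acidotic.

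**Cost of closing the gap.** At most 84 x 19 = 1,596 glucose results. If the baseline draw falls within the 72-hour pre-treatment window and also serves Cycle 1 Day 1, the count is 84 x 18 = 1,512. Patients who stop early reduce both figures.

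**What cannot be computed.** The documents give no rate of hyperglycemia and no asymptomatic share, so the number of missed holds is not estimated.

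**The case against.** The strongest case against is that the plan leaves some endocrine events to clinical detection by design. Three facts support it. Hypophysitis is also a hold row without all of its tests scheduled, so glucose is not a lone omission. Symptomatic or acidotic diabetes has routes to detection, and known diabetes should appear in the baseline history. Section 8.0 leaves responsibility for treating patients with the investigator, and nothing forbids a glucose test. All of this stands, and it limits the point to asymptomatic hyperglycemia and the missing baseline value. It does not supply the test.

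Several stronger readings are tempting, and the documents do not support them:

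- *Any Grade 3-4 glucose requires a hold.* The fuller cell in 8.3 requires evidence of beta cell failure. Only the short cell omits this, and the general laboratory rule in 8.2 can be read as referring back to the same table. A raised glucose prompts a work-up; it does not by itself meet the full condition.
- *Sites will not measure glucose.* The plan does not require it, which is a weaker statement.
- *Every laboratory list is defective.* Section 5.1.6, headed "Laboratory Requirements (must be done within 7 days prior to registration"), sets entry thresholds and is not a monitoring list. Section 9.2 also omits glucose, but no protocol dose remains to hold at that visit, although 12.2 lets patients continue the drug under standard care after one year.
- *Steroid use is certain to be on record.* Section 8.5.1 says: "All supportive medications must be recorded on the electronic case report form as appropriate". Steroids given for immune-related events appear in 8.5.2, so it is a reasonable inference, not stated text, that this instruction covers them.

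**Conclusion.** The gap is real and limited. The protocol states a dosing hold that depends on detecting hyperglycemia, yet its baseline, on-treatment and flow-sheet lists require 0 glucose results per patient. The liver and renal rows have up to 19 per analyte and the thyroid row up to 10. Asymptomatic hyperglycemia could therefore pass unseen before the next dose, and there is no scheduled baseline against which to judge new onset or relatedness.

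The counts assume a full year on the three-week schedule with no missed cycles. They measure scheduled testing, not harm.

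A reader might infer that the trial's main result is at risk. It is not: toxicity is a secondary objective, and the texture analysis uses neither glucose nor the hold rule. The change is worth making as a cheap safety improvement.

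**What to change.** 1. Add glucose to the chemistry already drawn at baseline and on Day 1 of each cycle, in 6.0, 9.1 and Appendix I. A random sample is acceptable.
2. State in 8.3 that a Grade 3-4 value prompts review of corticosteroid use and, if that does not explain it, assessment for beta cell failure or ketosis before the next dose.
3. Word the two cells of the 8.3 row consistently, so that it is clear whether beta cell failure is part of the trigger.
4. Say explicitly that corticosteroids given for immune-related events are recorded, since attribution depends on them.

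The cost is amendment wording and one analyte on existing blood: at most 19 results per patient, or 1,596 for 84 patients, with no added scheduled visit or draw. The downside is some extra abnormalities to grade and attribute, including steroid-related ones, and an occasional follow-up work-up.

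### The hypophysitis row in Section 8.3 says to hold pembrolizumab for Grade 2-4 but also permits it to continue, with no limit by grade or time, and no other text settles which applies

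*Combined protocol and SAP*

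**What the plan says.** The Section 8.3 table has a column headed "Hold Treatment For Grade" and, next to it, one headed "Timing for Restarting Treatment". Read across these two columns, the row begins "Hypophysitis 2-4 Toxicity resolves to Grade 0-1". The hold grades are in the first of them, and the Grade 0-1 condition opens the second. The restart cell then continues with two more sentences, in this order:

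- The second sentence of the cell is a permission to keep dosing: "Therapy with pembrolizumab can be continued while endocrine replacement therapy is instituted"
- The third sentence of the cell turns to the taper and refers to improvement: "When symptoms improve to grade 1 or less, steroid taper should be started and continued over no less than 4 weeks"

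The last column sets discontinuation if the toxicity has not resolved within 12 weeks of the last dose, or if the corticosteroid cannot be reduced to the stated level within 12 weeks.

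Three other places bear on the row:

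- **Hypothyroidism row, same table.** No hold grade is entered, and the text is "Therapy with pembrolizumab can be continued while thyroid replacement therapy is instituted".
- **Section 8.2.** Pembrolizumab is to be withheld for drug-related non-hematological toxicity of Grade 3 or higher. The section also has a rule for conflicts: "If a patient experiences several adverse events and there are conflicting recommendations, please use the recommended dose adjustment", meaning the one with the greatest hold or a discontinuation.
- **Note under the Section 8.3 table.** Any life-threatening event leads to permanent discontinuation.

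**The concern.** When endocrine replacement is started for a Grade 2-4 event, the hold column and the first sentence of the restart cell point to withholding the drug. The second sentence of that cell points to giving it. The trial is multicentre (Section 4.0), so it is foreseeable that one centre will hold and another will keep dosing, each relying on the same row.

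The first thing at stake is patient safety, because this is an instruction on whether to dose during an immune-related event. The second is consistency of record. Toxicity is a secondary objective (Section 1.2), and unacceptable toxicity as defined in Section 8.0 is a reason to stop protocol treatment (Section 12.1). If the row can be read two ways, neither the sites nor the central office can say reliably whether a dose given during Grade 2 hypophysitis was a deviation.

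**Working it through.** There is no stated figure to reproduce. The check sets the passages side by side.

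**1. The row against itself.**

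| Part of the row | Effect at Grade 2-4 |
|---|---|
| Hold column: 2-4 | Dosing stops |
| Restart cell, sentence 1 | Dosing resumes at Grade 0-1 |
| Restart cell, sentence 2 | Dosing may continue during endocrine replacement; no grade or time limit |
| Restart cell, sentence 3 | Steroid taper starts once symptoms reach Grade 1 or less |

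Sentence 2 comes before the cell describes improvement to Grade 1 or less. Nothing in it confines it to the period after a hold.

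**2. The row against its neighbours.** In the hypothyroidism row the parallel sentence stands with no hold grade, so it describes dosing without a hold. The pneumonitis Grade 2 entry has the same Grade 0-1 condition and the same taper sentence but no continuation sentence, and it is unambiguous. The diabetes row uses the word resume for restarting after a hold; the hypophysitis row speaks of continuing.

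**3. Does other text settle it, grade by grade?**

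- *Grade 2.* The Section 8.2 withholding rule for non-hematological toxicity starts at Grade 3, so it does not reach this grade. The Section 8.2 conflict rule is written for a patient with several adverse events, not for two statements about one event. A footnote to the Section 8.3 table leaves holding for intolerable or persistent Grade 2 events to the physician. No marker tying it to this row is visible, and it does not limit the continuation sentence. The conflict is unresolved.
- *Grade 3.* Section 8.2 requires withholding. The continuation sentence therefore conflicts with a second passage as well as with its own hold column.
- *Grade 4.* The same conflict with Section 8.2 applies. In addition, the row treats Grade 4 as hold and restart, while the table note requires permanent discontinuation for any life-threatening event. The documents describe Grade 4 as life-threatening in the infusion-reaction table (Section 8.3.1). Where a Grade 4 hypophysitis event is life-threatening, the row and the note disagree.

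**4. The 12-week limit.** The resolution limit runs from the last dose, and the schedule is one dose every 3 weeks (Section 8.1.1). If dosing continues on schedule, the time since the last dose never exceeds 3 weeks. Because 3 is less than 12, that limit cannot be reached while dosing goes on. The separate corticosteroid criterion has its own 12 weeks, with no stated starting point, and could still apply.

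**The case against.** The strongest reply is that the row can be followed without contradiction. The continuation sentence is a permission, not an order. A site that holds at Grade 2-4, restarts at Grade 0-1 and then doses while replacement is ongoing breaches nothing. The sentence sits under a heading about restarting, directly after the Grade 0-1 condition. The hypothyroidism row leaves the hold column empty, whereas hypophysitis has 2-4 there, which suggests that a hold was intended. Section 8.2 also links continuing the same dose to prompt resolution of symptoms, and its conflict rule leans toward the longer hold.

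Much of this stands. A reader might infer that sites cannot comply with both statements. That goes too far, because a site that holds complies with both. The problem runs one way: a site that keeps dosing departs from the hold while relying on a sentence in the same row.

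A reader might also infer that holds and doses for this event become uninterpretable. The documents do not support that. The Treatment Report records treatment and adverse events for every 3-week cycle (Appendix IV), and the central office monitors adverse events on an ongoing basis (Section 14.3), so what was given will be known. Only the classification as compliant or deviating is uncertain.

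The sequential reading does not dispose of the point, because it has to be supplied by the reader. The text does not state it, and the sentence order and the hypothyroidism wording point the other way. The Section 8.2 conflict rule shows a direction, but by its terms it does not apply to a single event.

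**Conclusion.** The point holds as a conflict of wording in a safety instruction. A site following the row literally can dose through hypophysitis that the row says to hold for. At Grade 2 no other passage resolves this. At Grade 3 or higher the permission also runs against Section 8.2, and at Grade 4 the hold-and-restart entry runs against the table note wherever the event is life-threatening.

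The size cannot be given in patients. The plan is to recruit 84 (Section 14.2), but the documents state no frequency for hypophysitis. The sample size and the primary analysis of CT texture against response do not depend on this row. The conclusion assumes that the extracted table preserves the row's cells and sentence order, and that no marker tying a footnote to this row was lost. It takes no view on which clinical rule is right.

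**What to change.** The sponsor should reconcile the hypophysitis row with its own hold column, with the Section 8.2 withholding rule and with the table note on life-threatening events, so that Grades 2, 3 and 4 each carry one instruction. The revised text should make clear when the continuation sentence applies relative to the hold, and from what point the 12-week limits run. The choice of rule belongs to the sponsor's clinical lead.

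The cost is a wording change to one table row in the next amendment and a memo to sites. No data collection, sample size or analysis needs to change.
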